#### 5.1.2 TARGET AND NORMAL STRUCTURE CONTOURING

Diagnostic CT scans and MRIs (if available) will be fused to the CT simulation for contouring purposes to help guide contouring of target and normal structures, which will be recorded on the CT images. Normal structures to be contoured include spinal cord, esophagus, heart, chest wall, body, stomach, duodenum, small bowel, large bowel, lung, liver, and kidneys.

The gross tumor volume (GTV) (or internal target volume (ITV) if 4-dimensional CT is utilized) will be contoured using all available images, and the planning target volume (PTV) will be constructed using a 5 mm circumferential margin. All participants must have a critical volume of liver minus GTV (or ITV) of at least 700 cm^3.

If tumor motion is greater than 3 mm, participants will be simulated and treated with a breathhold technique. In breathhold technique, the participant is treated in a specific inspiratory phase of the respiratory cycle. If appropriate and at the discretion of the treating physician, participants may also undergo a MRI simulation in the treatment position to assist in the contouring of tumor and normal structure. If performed, MRI should be done with contrast.

#### 5.1.3 RADIATION THERAPY

A total of 40 Gy will be administered to the PTV in 5 fractions given every other day, provided that normal organ constraints are met (i.e., uninvolved liver volume of  $\geq 700$  cc).

If normal organ constraints are not met, the dose will be iteratively de-escalated to two dose levels (35 Gy in 5 fractions, then 30 Gy in 5 fractions)(**Table 2**). If normal organ constraints are unable to be met at 30 Gy in 5 fractions, the patient is deemed ineligible for SBRT and is considered a screen failure. Cone-beam CT will be obtained prior to each fraction delivered.

**Table 2. SBRT – Dose Modification**

Dose Level	Liver-directed SBRT
0*	40 Gy in 5 fractions
-1	35 Gy in 5 fractions
-2	30 Gy in 5 fractions

\*Dose level -1 and -2 are treatment doses for patients requiring a dose reduction from the starting dose level (0).

#### 5.1.4 PLANNING CONSTRAINTS

Dose constraints for normal organs at risk including spinal cord, esophagus, heart, chest wall, skin, stomach, duodenum, small bowel, large bowel, lung, liver, and kidneys will be according to institutional standards for liver SBRT (**Table 3**).

**Table 3. Dose Constraints**

Serial Tissue	Volume	Volume Max (Gy)	Max Point Dose (Gy)**
CORD	0.1cc	25 Gy	30 Gy (6 Gy/fx)
	<0.35 cc	23 Gy (4.6 Gy/fx)	
	<1.2 cc	14.5 Gy (2.9 Gy/fx)	
Esophagus*	<5 cc	19.5 Gy (3.9 Gy/fx)	35 Gy (7 Gy/fx)
Heart/Pericardium	<15 cc	32 Gy (6.4 Gy/fx)	38 Gy (7.6 Gy/fx)
Chest wall/Rib	<30 cc	35 Gy (7 Gy/fx)	43 Gy (8.6 Gy/fx)
Skin	<10 cc	36.5 Gy (7.3 Gy/fx)	39.5 Gy (7.9 Gy/fx)
Stomach	0.1cc	27.5 Gy	32 Gy (6.4 Gy/fx)
	<10 cc	18 Gy (3.6 Gy/fx)	
Duodenum*	0.1cc	30 Gy	32 Gy (6.4 Gy/fx)
	<5 cc	18 Gy (3.6 Gy/fx)	
	<10 cc	12.5 (2.5 Gy/fx)	
Small bowel*	<5 cc	19.5 Gy (3.9 Gy/fx)	35 Gy (7 Gy/fx)
Large Bowel*	<20 cc	25 Gy (5 Gy/fx)	38 Gy (7.6 Gy/fx)
<hr/>			
Parallel Tissue	Critical Volume (cc)	Critical Volume Dose Max (Gy)	
Lung Total	1500 cc	12.5 Gy (2.5 Gy/fx)	
Lung Total	1000 cc	13.5 Gy (2.7 Gy/fx)	
Liver GTV	700 cc	15 Gy (3 Gy/fx)	21 Gy (major dev)
Kidney Total	200 cc	17.5 Gy (3.5 Gy/fx)	

\*Avoid circumferential irradiation

\*\* “point” defined as 0.035cc or less

The PI will perform RT Quality Assurance Reviews of all plans within 10 days of patients starting the treatment.

#### 5.2 DOSING DELAYS AND MODIFICATIONS

SBRT will be delivered in a total of 5 fractions over two weeks, with treatments delivered every other day between Monday and Friday. SBRT will not occur on Saturdays, Sundays or holidays. There should be no more than a 14 day interruption between the planned administration of each fraction. Dosing interruptions lasting longer than 14 days between each fraction, for any reason, are considered an unacceptable and participants will be removed from

study and replaced with another participant. Participants removed from study will be treated per institutional standards or offered participation in another clinical trial if one is available. All dosing interruptions should be recorded in CRF.

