### 4.6.1 HANDLING PARTICIPANT WITHDRAWAL AND DISCONTINUATION

Participants enrolled in this study that withdraw prior to initiating on-study treatment will be replaced.

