### 7.1 DEFINITION OF EFFICACY MEASURES

Evaluable for response. The analysis population to assess efficacy endpoints (e.g., local control rate, intrahepatic disease free survival, and overall survival), will include only participants who have received at least 85% of the prescribed SBRT dose (i.e., 85% Level 0 = 34 Gy; 85% Level -1 = 30 Gy; 85% Level -2 = 25.5 Gy). Participants that experience more than 14 days of dose interruption, after having received  $\geq$  85% of the prescribed SBRT dose will be included for analysis.

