### 9.1 ANALYSIS POPULATIONS

Safety analysis set: All participants will be evaluable for toxicity from the time of their first fraction of SBRT.

Efficacy analysis set: The analysis population to assess transplantation eligibility (i.e., Milan criteria) and efficacy endpoints (e.g., localized control rate, intrahepatic progression, extrahepatic progression and overall survival), will include only participants who have received at least 85% of the prescribed SBRT dose (i.e., 85% Level 0 = 34 Gy; 85% Level -1 = 30 Gy; 85% Level -2 = 25.5 Gy).

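### Section 5.2 replaces already irradiated participants after a gap over 14 days, and the plan does not settle whether they count in the primary denominator

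*Combined protocol and SAP*

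**What the plan says.** Four sections of the combined protocol and SAP bear on a participant whose course is interrupted.

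- **Section 5.2** sets the limit: "There should be no more than a 14 day interruption between the planned administration of each fraction". Beyond it, "Dosing interruptions lasting longer than 14 days between each fraction, for any reason, are considered an unacceptable and participants will be removed from" the "study and replaced with another participant". Later care is outside the protocol: "Participants removed from study will be treated per institutional standards or offered participation in another clinical trial if one is available".
- **Section 4.6.1** has a different replacement trigger: "Participants enrolled in this study that withdraw prior to initiating on-study treatment will be replaced". It does not mention participants who have started treatment.
- **Section 9.1** says the efficacy set "will include only participants who have received at least 85% of the prescribed SBRT dose". It gives thresholds of 34, 30 and 25.5 Gy for the three dose levels and has no interruption criterion. The safety set is everyone from the first fraction. Section 9.2.2 computes the primary proportion, with an exact 95% CI, in the efficacy set.
- **Section 7.1** repeats the 85% rule and adds a sentence that starts "Participants that experience more than 14 days of dose interruption, after having received" and goes on to say that those who had reached 85% of the dose are included.

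**The concern.** Section 9.3.1 gives the main purpose of this pilot as finding problems before a larger trial. A course that cannot be delivered on schedule is such a problem. Section 5.2 removes the person it happened to and brings in someone else. The selection is made on an event after treatment starts, and that event may be related to outcome: Section 5.3 lists treatment interruption among the measures for severe radiation-related symptoms.

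If the replacement takes the original participant's place in the analysis, the denominator shifts towards people who got through SBRT on time, and the reported proportion can be too high. With 15 participants, each one is worth 1/15 = 6.7 percentage points. The sections that should say who is counted do not give one answer.

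**Working it through.** **1. The plan's own thresholds.** 0.85 × 40 = 34 Gy, 0.85 × 35 = 29.75 Gy (printed as 30) and 0.85 × 30 = 25.5 Gy. These reproduce.

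**2. When 85% is reached.** Section 5.1.3 states: "A total of 40 Gy will be administered to the PTV in 5 fractions given every other day". Equal fractions are an assumption. It is supported by Table 3, whose per-fraction figures are totals divided by five (for example, 30 Gy is shown with 6 Gy per fraction). Cumulative dose after k fractions is then 20k%.

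| Level | Per fraction | After 4 fractions | 85% threshold | After 5 fractions |
|---|---|---|---|---|
| 0 | 8 Gy | 32 Gy | 34 Gy | 40 Gy |
| -1 | 7 Gy | 28 Gy | 29.75 Gy (printed 30) | 35 Gy |
| -2 | 6 Gy | 24 Gy | 25.5 Gy | 30 Gy |

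At every level, four fractions give 80%, so 85% is met only by the fifth and last fraction. Every between-fraction gap therefore falls before 85%, and the interruption sentence in 7.1 has nobody to apply to. For four fractions to reach 85% at level 0, the last one would have to be 40 − 34 = 6 Gy or less, against 8 Gy under equal fractionation.

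**3. Where a participant with a gap over 14 days ends up.**

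| Case | 5.2 | 85% rule (9.1, and the same rule in 7.1) |
|---|---|---|
| Receives all five fractions; dose after removal counts | Removed, replaced | In (100%) |
| Receives all five fractions; dose after removal does not count | Removed, replaced | Out (80% at most) |
| Stops at four fractions or fewer | Removed, replaced | Out (80% at most) |

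The documents do not say which of the first two rows applies. In the first row, 9.1 would keep the original participant alongside the replacement, so the denominator would exceed the planned number. In the other two rows the replacement takes the place of a treated person.

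**4. Possible size.** The documents give neither a gap rate nor an expected success rate, so these are assumed illustrations. Take x successes in a set topped up to 15, then put back k replaced participants as non-successes, giving x/(15 + k). Exact (Clopper-Pearson) 95% CIs are in brackets.

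| k | x = 12 | x = 9 |
|---|---|---|
| 0 | 12/15 = 80.0% (51.9 to 95.7) | 9/15 = 60.0% (32.3 to 83.7) |
| 1 | 12/16 = 75.0% (47.6 to 92.7) | 9/16 = 56.2% (29.9 to 80.2) |
| 2 | 12/17 = 70.6% (44.0 to 89.7) | 9/17 = 52.9% (27.8 to 77.0) |
| 3 | 12/18 = 66.7% (41.0 to 86.7) | 9/18 = 50.0% (26.0 to 74.0) |

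This is the worst case. If one of two restored participants were a success, 12/15 would become 13/17 = 76.5%. If both were, it would become 14/17 = 82.4%.

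**The case against.** The strongest reply is that 5.2, read strictly, leaves little conflict. A participant with a long gap leaves the study, and any later fractions are given off study. If only on-study dose counts, that person has at most 80% and is outside the efficacy set under both 7.1 and 9.1, consistent with removal. This is a fair reading, but the plan does not state it. It also concedes the main point, because a treated participant is then dropped from the primary analysis and replaced.

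Two stronger readings are tempting, and the text supports neither.

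- A reader might infer that 7.1 excludes a late completer. Its base rule is the same as that in 9.1, and its interruption sentence only includes people. Exclusion would be a negative inference.
- A reader might infer that 4.6.1 forbids replacing treated participants. It does not restrict replacement to the pre-treatment case; 5.2 can stand as a second trigger. The two sections are poorly aligned but not in direct contradiction.

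Other points stand in part. Nothing in the documents shows that gaps over 14 days mostly reflect decompensation, and 5.2 covers every cause. Sections 6.4 and 6.8 limit visit delays to 7 days, so such gaps may be rare. The intervals above overlap heavily, and no hypothesis test is planned. Replaced participants stay in the safety set, and interruptions are recorded in the CRF, so toxicity reporting is protected and the information is not lost.

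**Conclusion.** The concern holds in this form. Section 5.2 replaces irradiated participants on a post-treatment event. Section 9.1 has no matching rule, and the 7.1 sentence that might have linked them cannot operate with five equal fractions. Whether a late completer is in the primary denominator depends on an unstated convention about dose given after removal.

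The direction of bias is upward if participants with long gaps do worse than their replacements. That is plausible but not shown. The size is unknown. On the assumed worst case from 12/15, the reported 80% would fall by 5, 9 or 13 points for one, two or three restored participants, and by less if some remain transplant eligible. The conclusion rests on equal fraction size and concerns the primary and other efficacy estimates, not the safety set. It should be corrected, because the preliminary proportion is the pilot's main output.

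**What to change.** For analysis purposes:

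1. State that a replacement never takes the place of anyone who received at least one fraction.
2. In 9.1 and 9.2.2, report the primary proportion with its exact CI in all participants who started SBRT, alongside the 85%-dose set. Use available follow-up and count those without documented success as non-successes. Write this convention into the endpoint definition so that it does not clash with the no-imputation rule in 9.4. This analysis also covers participants who stop at 80% or less, whom the 85% rule alone would drop.
3. State in 9.1 whether dose given after removal counts towards 85%.
4. Delete the interruption sentence in 7.1, or rewrite it so that it can apply.
5. Report the number of participants with gaps over 14 days as a feasibility result.

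The clinical handling of interruptions in 5.2 is for the sponsor to reconcile with 4.6.1, 7.1 and 9.1.

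The cost is wording in these sections, one extra analysis and possibly a lower reported proportion.

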### 5.3 CONCOMITANT MEDICATION AND SUPPORTIVE CARE GUIDELINES

Supportive measures for optimal medical care are to be given throughout the study as indicated by the treating physician's assessment of the participant's medical need and institutional and general medical guidelines for the care of participants undergoing treatment of HCC.

Supportive care guidelines for radiation therapy are described in Table 4. Additional supportive care procedures and any premedications, according to institutional guidelines, include hydration, pain management, anti-emetics, and treatment interruption in case of severe radiation-related symptoms.

Table 4. Supportive care guidelines for radiation therapy

Adverse effect	Support Treatment
Psychological	
Depression:	Selective serotonin reuptake inhibitors effective for depression but not for fatigue
Fatigue:	Exercise; sleep hygiene, stress reduction, cognitive and relaxation therapies
Skin	
Dermatitis:	Moisturizing creams; routine skin care with mild, unscented soap
Radiation recall:	Same as dermatitis
Cardiovascular and pulmonary	
Cardiovascular disease:	Cardiovascular monitoring (ECG)
Gastrointestinal	
Diarrhea	Loperamide
Genitourinary	
Urinary obstruction	Tamsulosin (for males) administered according to institutional guidelines
Cystitis:	Pyridium (both males and females) administered according to institutional guidelines
Infertility / teratogenicity:	Egg and sperm preservation; ovarian transposition

#### 5.3.1 CONTRACEPTION

SBRT may have adverse effects on a fetus in utero, and may have adverse effects on the composition of sperm. People may be enrolled if they are willing to use methods of birth control or are considered highly unlikely to conceive. Highly unlikely to conceive people are defined as: 1) surgically sterilized or biologically absent reproductive organs, or 2) postmenopausal (a woman who is  $\geq$  45 years of age and has not had menses for more than 1 year), or 3) not heterosexually active for the duration of the study. Birth control methods can either be two barrier methods or a barrier method plus a hormonal method to prevent pregnancy. Participants should start using birth control from study visit 1 throughout the study period up to 120 days after the last dose of study therapy.

### 5.3.2 USE IN PREGNANCY

If a participant inadvertently becomes pregnant while receiving SBRT, the participant will immediately be removed from the study. The site will contact the participant at least monthly and document the participant's status until the pregnancy has been completed or terminated. The site will report the outcome of the pregnancy to Sponsor without delay and within 24 hours if the outcome is a serious adverse experience (e.g., death, abortion, congenital anomaly, or other disabling or life-threatening complication to the mother or newborn). The pregnancy will be recorded on the CRF and reported by the Investigator to the IRB. Refer to Section 8.6.

## 5.4 PROHIBITED MEDICATIONS, TREATMENTS, AND PROCEDURES

Herbal supplements will be allowed on study and noted on CRF. For patients with contrast allergy, steroids will be allowed for CT scans.

Participants are prohibited from receiving the following therapies during the Screening and Treatment Period of this trial:

- Anti-cancer systemic chemotherapy or biological therapy.
- Chemotherapy not specified in this protocol.
- Investigational agents other than those described in this protocol.
- No radiation therapy other than what is allowed in this study.

Participants who require the use of any of the aforementioned treatments for clinical management may, at the discretion of the investigator, be removed from the trial. Participants may receive other medications that the investigator deems to be medically necessary.

Participant exclusion criteria (Section 4.2) describes other medications prohibited in this trial.

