#### 3.2 STUDY ENDPOINTS

##### 3.2.1 PRIMARY ENDPOINT

Endpoint	Start	End
Proportion of participants who are transplanted or with localized disease control that meets Milan criteria (Section 7.5) within 1 year	Start of SBRT	Time of progression, or transplantation, or 1-years after last SBRT dose, whichever occurs first

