## 4.6 PARTICIPANT WITHDRAWAL OR DISCONTINUATION

Participants are free to withdraw consent and discontinue participation in the study at any time and without prejudice to further treatment. If a participant no longer wants to receive investigational product, but is willing to come for follow-up appointments, the participant's request should be honored, if possible. The following are examples demonstrating why a participant's treatment might be discontinued.

- Toxicity precludes further study treatment.
- There is a need for any treatment not allowed by the protocol.
- The participant fails to meet the criteria for study treatment.
- Pregnancy or intent to become pregnant.
- Disease recurrence or progression.
- Investigator's discretion.

No further participant contact should be made if the participant withdraws consent for participation in the study. Information about the reason(s) for discontinuation and collection of any new or ongoing adverse events (AEs) should be collected at the time the participant withdraws consent.

For all other reasons for discontinuation from the study treatment phase, the participant should return to the clinic for the end of treatment (EOT) visit according to Section 6.8.

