## 5. TREATMENT PLAN

### 5.1 DOSAGE AND ADMINISTRATION

On-study treatment will be administered on an out-patient basis. Reported adverse events and potential risks are described in Section 8.4. Appropriate dose modifications are described in Section 5.2, Dose modifications. No investigational or commercial agents or therapies other than those described below may be administered with the intent to treat the participant's malignancy.

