### 7.3.3 LOCAL CONTROL RATE

Local control is defined as the absence of progressive disease (per Section 7.3.1) within the PTV or at the PTV margin, measured from time of first SBRT dose to time of progression or transplantation, or 2 years from last SBRT dose, whichever occurs first.

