#### 9.2.4 ANALYSIS OF THE EXPLORATORY ENDPOINT

The QoL scores will be recorded over time (See Sections 6.1.8 and 6.8) using the EORTC QLQ-C30 and FACT-Hep questionnaires. Summary of QoLs and its change over time will be presented graphically using box plot and spaghetti plot, in addition to a summary table of QoL over time. No hypothesis testing is planned for QoL.

Descriptive statistical analysis, utilizing the efficacy analysis set, will be used to measure the proportion of histopathologic changes in irradiated tumor sites relative to uninvolved liver tissue will be measured.

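### No rule says how other HCC therapy after SBRT is counted, so the 1-year eligibility proportion can credit SBRT with control obtained by another treatment

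*Combined protocol and SAP*

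**What the plan says.** **Restrictions.** Section 5.1 states, under on-study treatment, "No investigational or commercial agents or therapies other than those described below may be administered with the intent to treat the participant's malignancy". No period is given. Section 5.4 states "Participants are prohibited from receiving the following therapies during the Screening and Treatment Period of this trial" and then lists systemic or biological anti-cancer therapy, chemotherapy, investigational agents and other radiation. TACE/TAE and ablation are not named. Participants who need a listed treatment "may, at the discretion of the investigator, be removed from the trial". Section 4.6 includes "There is a need for any treatment not allowed by the protocol" among its examples of why treatment might be stopped, and attaches no endpoint consequence.

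**Primary endpoint.** Section 3.2.1 defines it as "Proportion of participants who are transplanted or with localized disease control that meets Milan criteria (Section 7.5) within 1 year" and closes the window at progression, transplantation or 1 year after the last dose. Section 9.2.2 and the synopsis instead use transplant eligibility at 1 year and make no mention of progression.

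**Other endpoints.** Local control (7.3.3) is "measured from time of first SBRT dose to time of progression or transplantation, or 2 years from last SBRT dose, whichever occurs first". Section 9.2.4 describes the "proportion of histopathologic changes in irradiated tumor sites relative to uninvolved liver tissue" found at transplantation. In none of these does the start of another HCC therapy end a window, count as an event or cause censoring. The analysis sets (9.1) and the missing-data section (9.4) do not address it either.

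**Data capture.** Section 6.1.3 asks for medications before SBRT starts. The schedule in 6.8 has a row for prior and concomitant medications that extends into follow-up, but no row for procedures.

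**The concern.** The trial has one arm, and its primary objective asks whether SBRT gives enough local control to keep patients eligible for transplantation. Section 1.3 says the result will be used to estimate bridging efficacy against historical controls and to shape a larger trial. If some participants stay eligible only because another treatment was added, the proportion describes SBRT plus that treatment, with no comparator to separate them. Other HCC therapy would tend to be given where control looked inadequate, so counting those participants as plain successes can only leave the figure unchanged or raise it above the proportion of successes on SBRT alone. If date, type and treated lesion are not recorded at the time, the two groups may not be separable afterwards.

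**Working it through.** **Step 1. Scope of the restrictions.** SBRT takes about 10 days (synopsis). The primary window is 1 year and the local-control window 2 years. Section 5.4 therefore covers little of either window and omits TACE/TAE and ablation throughout. Section 5.1 is wider in kind, but its reach into follow-up is unclear. Neither section decides whether such therapy is allowed after SBRT, and neither says how it would be counted.

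**Step 2. Classification under the two primary-endpoint texts.** Section 9.2.2 mentions only Milan eligibility. It is read here with 3.2.1 as including those already transplanted.

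| Other HCC therapy given | 3.2.1 | 9.2.2 and synopsis endpoint |
|---|---|---|
| Before or without declared progression; then transplanted or within Milan at 1 year | Window still open: success | Success |
| After declared progression; within Milan at 1 year | Window already closed: later status not counted on a plain reading | Success |

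**Step 3. Can therapy precede declared progression?** Yes, by two routes.

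- Section 7.3.1 requires at least a 20% rise in the summed viable diameters. An irradiated lesion that still enhances but has grown less than 20% can be treated with no progression on record, and 7.3.3 continues to count local control.
- Under 7.3.2.1, a nodule of 10 mm or more with atypical enhancement can be diagnosed as HCC only after further growth. If it is ablated first, progression may never be declared.

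By contrast, a new 1.5 cm nodule with typical enhancement is progression under 7.3.2.1 and falls in the second row of the table.

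**Step 4. Size.** The only planning figure is N = 15 (9.3.1), for seeing at least one dosimetrically ineligible patient when p = 0.20. The formula n = ln(0.05)/ln(0.80) = 13.4 gives 14, and at 15 the probability is 1 − 0.80^15 = 0.965. So 15 is adequate for that aim, and it does not depend on this point.

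For the primary proportion, one participant is 1/15 = 6.7 points if all 15 are analysed, and more if fewer are. As an assumed illustration, take 10 successes as planned, of whom k had other HCC therapy. Exact (Clopper-Pearson) 95% intervals are:

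| k | Successes without other therapy | Estimate | 95% CI |
|---|---|---|---|
| 0 | 10/15 | 66.7% | 38.4 to 88.2 |
| 1 | 9/15 | 60.0% | 32.3 to 83.7 |
| 2 | 8/15 | 53.3% | 26.6 to 78.7 |
| 3 | 7/15 | 46.7% | 21.3 to 73.4 |

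The documents give no rate of other therapy. At assumed rates r of 10%, 20% and 30%, the chance of at least one case among 15, 1 − (1 − r)^15, is 0.794, 0.965 and 0.995. A rule may therefore be needed even if such therapy is fairly uncommon.

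**The case against.** The strongest reply is that the endpoint windows already deal with rescue. A new typical nodule is progression, progression closes the windows in 3.2.1, 3.2.2, 7.3.3 and 7.3.4, and 4.7 lists it as a reason to go off study. The synopsis also ends follow-up there. Therapy after progression therefore cannot restore intrahepatic progression-free survival or, on a plain reading, the 3.2.1 endpoint. This stands, and it rules out the broad inference that every rescued participant is a success under every text. It does not reach therapy given before or without progression. Nor does it settle the primary analysis, because 9.2.2 has no progression condition and 6.5 continues visits to hospice, death or 2 years.

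A reader might also infer that failures can be removed selectively. The documents do not support this. The removal clause in 5.4 covers only its listed treatments, which do not name TACE/TAE or ablation, and 9.1 fixes the efficacy set by receipt of at least 85% of the prescribed dose. Leaving the trial does not by itself change that denominator.

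Sections 5.1 and 5.4 could be read as a flat contradiction. They are better described as differing in scope, with the duration of 5.1 left unclear.

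On size, section 1.2 says TACE is generally not used in Child-Pugh C or late B disease, and 1.1 says many patients with advanced cirrhosis are excluded from liver-directed therapy. A 20-point shift (three of 15) has no basis in the documents. The study also has no hypothesis test or success threshold for a shift to cross. These points limit the likely effect, but they do not supply the missing rule.

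Finally, calling such therapy a local failure would be one choice among several and would replace the 7.3.3 definition. That is accepted: the fix asks for sensitivity analyses only. The explant analysis is descriptive and exploratory, so a flag is enough there.

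**Conclusion.** The concern holds in this limited form. Other HCC therapy after SBRT has no stated handling in any endpoint or analysis section. When it comes before or without declared progression, a participant later transplanted or within Milan at 1 year is a success under both 3.2.1 and 9.2.2. When it follows progression, the two sections conflict and the participant is a success under 9.2.2, provided 1-year status is still obtained.

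Each such success is worth 6.7 points if 15 are analysed. How many there will be is unknown and may be zero. The count of successes without other therapy is a subset of the planned count over the same denominator, so the planned figure can only equal or exceed it. The lower figure is not a pure effect of SBRT either, since some of those treated might have stayed eligible without the extra therapy. Reporting both shows how far the result depends on it. The sponsor should make this change, because following 9.2.2 as written would credit SBRT with another treatment's effect in the estimate meant to inform the next trial.

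**What to change.** 1. Reconcile 5.1 with 5.4 on which therapies are covered and for what period; this review takes no position on what that rule should be. Reconcile 3.2.1 with 9.2.2 and the synopsis on whether progression before 1 year precludes success.
2. Record date, type, treated lesion and reason for every non-protocol HCC therapy, procedures included, through the 1- and 2-year windows.
3. In 9.2.2, report the primary proportion with its exact 95% CI in two ways: as planned, and counting as successes only participants with no other HCC therapy after SBRT.
4. Keep the 7.3.3 definition for the main local-control analysis. Add a sensitivity analysis for non-protocol therapy to a lesion in or at the margin of the planning target volume, for example taken once as an event and once as censored on that date.
5. Flag explants from participants who had other therapy to the irradiated site.

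The cost is protocol and analysis wording plus one CRF item, with no added visits or participants. The drawback for the sponsor is a second figure that will be equal to or lower than the one now planned.
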